The NSS-2 BRIDGE (Appendix 1) is a battery operated and disposable percutaneous auricular nerve field stimulator (Innovative Health Solutions, Versailles, IN, USA), that was recently cleared by the FDA and assigned a Class II Risk Designation; a class which includes surgical drapes, pumps and power wheelchairs. The indication for the NSS-2 BRIDGE is for the treatment of clinical symptoms related to opioid consumption and opioid withdrawal. These symptoms include abdominal pain, anxiety and post-operative nausea and vomiting; conditions which are also present following Cesarean-Section surgery. The use of the NSS-2 BRIDGE device has been demonstrated to provide significant analgesia in patients with abdominal pain syndrome, and clinical trials are ongoing to assess the benefit of this approach for post-operative pain management. As compared to the present use of opioids for perioperative pain management, the use of a complementary, non-pharmacologic approach offers the advantage of analgesia without the associated side effects. This is especially true in the post Cesarean Section population, in that many of these women want to breast feed and because of this are very motivated to not use opioids and other analgesics, allowing us to explore the additional benefits of non-pharmacological complementary pain management techniques.

Mechanism of action of the Auricular Percutaneous Electrical Nerve Field

The NSS-2 BRIDGE device allows for stimulation to branches of Cranial Nerves V, VII, IX and X, and the occipital nerves, identified by transillumination. Such a stimulation is transmitted to the central nervous and especially the limbic system, which is known to be a key component of the central nervous system response to stress, anxiety and the pain pathway. The nucleus involved by the stimulation include the amygdala (structure involved in the response to fear and anxiety), the thalamus (structure

involved in the management of visceral and somatic pain, addiction), the nucleus of tractus solitarius (structure involved in the control blood pressure) etc.... The stimulation of these nucleus produces a decrease in the transmission of pain impulses from visceral and/or somatic structures to supraspinal areas, a reduction in anxiety and control of blood pressure and associated changes of the sympathetic and parasympathetic nervous system.

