The primary end point will be the frequency of patients who experience an excellent tolerability along with a decrease of at least 20% in pain score. Also pain score and opioid consumption will be compared to data obtained 5 consecutive who underwent a C-section the month before.

Specific Aims

Specific Aims:

1. Tolerability and feasibility of applying the device following Cesarean Section
2. Look at the trend of opioid consumption and pain in five post- Cesarean section women wearing device, compared to five historical consecutive controls of women who underwent cesarean section in January 2019

Study Design

The proposed pilot study will be conducted as a single-center prospective open-label trial at the University of Pittsburgh Medical Center (UPMC) Magee-Womens Hospital. The data collected during this period will be compared to historical controls who have had elective C-Sections in the period of January, 2019. Institutional review board approval will be obtained before eligible patients are recruited and consented. Trial will be registered at www.clinicaltrials.gov before beginning recruitment.

Recruitment

Potential subjects will be recruited in the Magee Womens Hospital obstetrical unit when they arrive for elective Cesarean Section surgery. The Principal Investigator, [name] [name], will already have access to these patients as their primary OB Anesthesiologist. Patients will be asked for their interest in pursuing a research study that involves wearing a percutaneous, auricular field stimulator for five days as a supplementary method of post-operative pain control after their Cesarean-Section. Patients who agree to participate in the trial will sign an IRB approved Informed Consent Form.

Inclusion Criteria:

Over 18 years of age

Elective Cesarean-Section Surgery

Exclusion Criteria:

History of active depression, anxiety or catastrophizing

Active alcoholism or drug abuse

Severe chronic pain condition that requires daily preoperative opioid dependence

History of hemophilia

Patients with cardiac pacemakers

Patients with psoriasis vulgaris diagnosis

Data Collection and Outcome Measures

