The primary purpose of this pilot study is to demonstrate feasibility/acceptability of the NSS-2 Bridge device applied after a C-section. If the acceptability is confirmed, the C-section model will be included in an RFA NIH request (RFA-NS-19-018: HEAL Initiative: Clinical Devices to Treat Pain (UH3 Clinical Trial Optional) DEADLINE IS MARCH 8, 2019) for proposal related to the use of devices for reduction of opioid use. In this pilot, no changes will be made in the other analgesia/postpartum care. Potential subjects will

be recruited in the Magee-Womens Hospital obstetrical unit when they arrive for cesarean delivery. Patients will be asked if they are interested in using the NSS-2 Bridge system as a way to control pain after the C-section. They will offer to review a video explaining the mechanism of action of the NSS-2 Bridge system. Subject will be informed of the purpose of this pilot evaluation and if they agree to participate in the trial, they will sign an IRB approved Informed Consent Form.

Once patient has given and signed informed consent to participate in the study, demographic information and medical history will be collected from each participant on the day of the C-section. Data will be de-indemnified and kept in a lock cabinet. The NSS-2 BRIDGE device will be applied to one ear by trained research staff in the immediate post-operative setting. The patient will be informed at the time of consent and after the implantation of the device that they can have the device removed any time after its application.

As per standard of care, at 12, 24, 48, 72, 96 and 120 hours post-operatively will be collected pain score at rest and movement, total opioid consumption, as well as the device tolerability. Additionally as per other pain pilot IRB approved projects, we shall also collect common medical information including time to bowel movement, PONV, time to oral intake (liquid and regular diet), time to hospital discharge, intensive care unit (ICU) admission, readmission to the hospital, readmission due to pain related issues, quality of recovery after cesarean delivery, overall patient satisfaction, and patient satisfaction related to pain management. When the patient is discharged from the hospital, they will be asked to complete a patient satisfaction survey. For patients discharged with the device attached, removal instructions will be given to patient to remove and dispose of the device at 120 hours.

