Standard opioid conversion table will be used to convert the oral and IV narcotic utilized by the patients to IV morphine equivalent doses (MED) for analysis purposes.

Overall patient satisfaction and satisfaction of pain management during hospitalization will be measured by a numerical rating scale with 0- worst satisfaction and 10 being the best satisfaction. The patient satisfaction test will be administered by a member of the research team.

No statistical analysis will be performed. The primary end point will be the frequency of patients who experience an excellent tolerability along with a decrease of at least 20% in pain score. Also pain score and opioid consumption will be compared to data obtained 5 consecutive who underwent a C-section the month before

Pre-and-Post Metric Evaluation

The use of a non-pharmacological NSS-2 BRIDGE has the possibility of providing analgesia to post-surgical patients and reducing the number of opioids required following Cesarean-Section surgery. This will significantly impact patient outcomes, as patients will experience fewer opioid-related side effects (such as respiratory depression, post-operative nausea and vomiting, constipation and delirium, as well as transfer of opioids to the breast milk). This will also impact clinicians caring for post-operative patients, as there is the real potential they will have fewer conditions to monitor and treat as the patient recovers from surgery. The projected number of patients served by this project will initially be five (5) enrolled participants at Magee-Womens Hospital however, the data collected from this trial will serve countless patients and the community at large as physicians strive to move away from opioid use following surgery. Data collected from this pilot study will support a future proposal to the National Institute of Health (NIH) to fund a full-scale, randomized, placebo-controlled trial using the NSS-2 BRIDGE device.

Perhaps most importantly, the investigative use of the non-invasive NSS-2 BRIDGE device has the ability to significantly increase patient satisfaction in individuals who are opioid naïve or adverse to taking opioids as a method of pain control. Being able to offer the post-partum patients at Magee

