Womens Hospital of UPMC such an alternative represents a great opportunity to increase patient satisfaction, outcomes and compliance as many patients increasingly fear the use of opioids. The NSS-2 BRIDGE will remain effective on the participant for five days, and will have lasting effects even after discharge from the hospital, which is a time when many patients turn to opioids to control pain. The way the efficacy of this device will be measured will be by comparing total perioperative opioid consumption between study participants (n=5) historical controls who have had C-Sections at Magee Womens hospital in January 2019. Other outcome measures include the incidence of respiratory depression, PONV, constipation and length of stay between the study group and historical control group.

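### The opioid comparison sets women who opted in to a non-drug pain device against controls who were never asked, so it cannot measure the device's efficacy

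*Protocol*

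**What the plan says.** Entry to the device group is described twice in the Protocol. Recruitment says: "Patients will be asked for their interest in pursuing a research study that involves wearing a percutaneous, auricular field stimulator for five days". Data Collection and Outcome Measures says: "Patients will be asked if they are interested in using the NSS-2 Bridge system as a way to control pain after the C-section". Women are also offered a video on how the device works, and those who agree sign consent.

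The control group is formed differently. Under Specific Aims, Aim 2, the participants are to be "compared to five historical consecutive controls of women who underwent cesarean section in January 2019". These are past patients, so no offer was made to them and no interest was expressed.

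Two statements bear on who may volunteer. In the device description under Project Aims/Goals, the protocol says of the post-cesarean population that "many of these women want to breast feed and because of this are very motivated to not use opioids and other analgesics". Pre-and-Post Metric Evaluation expects the device to "significantly increase patient satisfaction in individuals who are opioid naïve or adverse to taking opioids as a method of pain control".

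The last paragraph of Pre-and-Post Metric Evaluation then fixes the use of the comparison: "The way the efficacy of this device will be measured will be by comparing total perioperative opioid consumption between study participants (n=5) historical controls", the controls being women delivered by cesarean in January 2019.

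The protocol describes no matching, no adjustment and no interest filter for the controls, and says that no statistical analysis will be done. Neither breast-feeding nor opioid preference is named among the data to be collected.

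**The concern.** One group is filtered by interest in a non-drug method of pain control and the other is not. The protocol itself supplies a reason why that interest could go with lower opioid use: a wish to avoid opioids, often because of breast-feeding. If volunteers hold that wish more often than unselected women, they would be expected to use less opioid even with an inert device.

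Giving the controls the same eligibility criteria would not remove this, because preference is not a criterion. Standard analgesia is left unchanged, which holds the offered care constant but not the patient's inclination to use it.

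At stake is what the pilot may claim. The text calls the opioid comparison the measure of efficacy and says that the pilot data will support a future NIH proposal. A difference between volunteers and non-volunteers could enter that proposal as a device effect.

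**Working it through.** The protocol gives no power, effect size, standard deviation or share of opioid-avoiding women, so there is no figure of its own to reproduce. The check has three parts.

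**1. Entry routes side by side**

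| | Device group | Controls |
|---|---|---|
| Number | 5 | 5 |
| Route | Asked on arrival, interested, consented | Consecutive past patients |
| Offered the device | Yes | No |
| Preference for avoiding opioids recorded | Not listed | Not listed |

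The groups differ in how they were selected before the device is applied, and nothing in the plan removes or measures that difference.

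**2. Expected spurious difference with an inert device**

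All inputs are assumptions. Let qD and qC be the shares of opioid-avoiding women in the device and control groups, and r the relative reduction in an avoider's use. Mean use relative to a non-avoider is 1 − r·q, so

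spurious reduction = 1 − (1 − r·qD)/(1 − r·qC).

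| qC | qD | r = 0.2 | r = 0.3 | r = 0.5 |
|---|---|---|---|---|
| 0.5 | 0.5 | 0% | 0% | 0% |
| 0.5 | 0.7 | 4.4% | 7.1% | 13.3% |
| 0.5 | 0.9 | 8.9% | 14.1% | 26.7% |
| 0.3 | 0.8 | 10.6% | 16.5% | 29.4% |
| 0.3 | 1.0 | 14.9% | 23.1% | 41.2% |

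Worked example: qC = 0.5, qD = 0.7, r = 0.3 gives 1 − 0.79/0.85 = 7.1%. Largest case: 1 − 0.50/0.85 = 41.2%.

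The sign depends on the shares. If volunteers held fewer avoiders (qC = 0.5, qD = 0.3, r = 0.3), the result is 1 − 0.91/0.85 = −7.1%: the device group would look worse.

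**3. Chance at 5 versus 5**

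The standard error of a difference in means is √(2/5) = 0.632 standard deviations. With an assumed coefficient of variation (CV) of 0.5 or 1.0, that is about 32% or 63% of the mean.

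A simulation with log-normal use, an inert device and 200,000 runs per setting gave:

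- No enrichment: the device mean is the lower one in 50% of runs. It is at least 20% lower in 24–28% of runs at CV 0.5 and in 35–36% at CV 1.0.
- Enriched settings of the table: the device mean is the lower one in 53–94% of runs.

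So a reduction of 20% or more can readily arise from selection, from chance or from both, with no device effect.

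**The case against.** The strongest case on the other side has four parts.

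- **Enrichment is inferred.** The motive to avoid opioids is attributed to post-cesarean women in general, which includes the controls. The remark about opioid-averse individuals concerns their satisfaction, not who volunteers. This stands: enrichment is plausible but not documented.
- **Selection could run the other way.** Women are asked about a way to control pain, not about avoiding opioids. Those expecting worse pain could also volunteer, and then use more. This stands too, so the net direction is open.
- **The link to use is partly assumed.** The protocol does not describe how opioids are given or how far the amount depends on the patient's request, and total perioperative use may include opioid not given on request. This stands; r in the table is purely illustrative.
- **The pilot's purpose is limited.** Its primary purpose is feasibility and acceptability, and Aim 2 only looks at a trend. No test is planned. Inclusion in the NIH request depends on acceptability, and the proposed trial is randomized and placebo-controlled. Volunteer selection comes with any consented single-arm pilot using historical controls. This lowers the weight of the point but does not answer it, because the efficacy sentence remains and the pilot data are still meant to support the proposal.

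**Conclusion.** The point holds as a limit on interpretation. Opt-in volunteers are compared with women who were never asked, on an outcome that the protocol's own account links to a plausible motive for volunteering, and the result is labelled efficacy. The design does not support that label.

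The size is not known. The 0% to 41% range rests wholly on assumed shares (30–50% avoiders among controls, 50–100% among volunteers) and an assumed 20–50% lower use among avoiders. Sampling error at this sample size is of the same order.

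A reader might infer that the device group is enriched and that the comparison would therefore favour an inert device. The documents do not establish that: they give no share for either group and say nothing of how volunteers differ from other women. Nor do they show that a favourable opioid result would decide whether the NIH request goes ahead. The primary feasibility aim, as distinct from the efficacy claim, does not depend on this comparison.

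**What to change.** 1. In the last paragraph of Pre-and-Post Metric Evaluation, replace the efficacy wording with a descriptive comparison, and put the same caveat in Aim 2. For example: *Opioid use in the five participants will be listed beside that of five consecutive January 2019 controls, for description only. Any difference may reflect volunteer selection, including a prior wish to avoid opioids, as well as chance. It will not be read as an effect of the device or cited as evidence of efficacy in the NIH proposal.*
2. Where the chart records it, list breast-feeding status beside opioid use for both groups, descriptively. Keep the consecutive control series and do not match: with five per group, matching would balance only a proxy and would give up the simple consecutive rule.
3. Do not add a question on intention to avoid opioids. The controls cannot answer it, and asking could itself influence use in the device group only.

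The cost is a wording change and one chart item per woman, with no extra patients. The downside is that the opioid result is presented less favourably. The caveat does not remove the bias; the randomized, placebo-controlled trial that the protocol foresees would.

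### Standard of care is the only named route to pain, opioid and tolerability data up to 120 h. It does not reach women who go home wearing the device, so late tolerability and early removal at home are not secured.

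*Protocol*

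**What the plan says.** Data Collection and Outcome Measures sets six time points and names one source for the data: "As per standard of care, at 12, 24, 48, 72, 96 and 120 hours post-operatively will be collected pain score at rest and movement". The sentence continues with "total opioid consumption, as well as the device tolerability".

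The same section provides for women who leave hospital before the end of wear: "For patients discharged with the device attached, removal instructions will be given to patient to remove and dispose of the device at 120 hours". The one contact it describes at that moment is a survey: "When the patient is discharged from the hospital, they will be asked to complete a patient satisfaction survey". The pain item of that survey concerns the hospital stay. Women are also told that they may have the device taken off at any time.

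Under Recruitment, women are asked about "wearing a percutaneous, auricular field stimulator for five days". The primary endpoint, given twice in the protocol, is "the frequency of patients who experience an excellent tolerability along with a decrease of at least 20% in pain score". Neither statement gives a time point. Pre-and-Post Metric Evaluation says that the device "will have lasting effects even after discharge from the hospital, which is a time when many patients turn to opioids to control pain". No usual length of stay appears anywhere.

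**The concern.** One section names a collection route and also describes the situation in which that route stops working. Routine ward care can supply ratings while a woman is an inpatient. It cannot supply them once she is at home, and no call, diary, visit, home opioid log or return of the device is described. Because the device is thrown away, the hour of removal cannot be checked afterwards.

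Tolerability is one of the two components of the primary endpoint, and acceptability is the stated purpose of the pilot. Taking the device off early is a direct sign of poor tolerability and is allowed, yet at home it would leave no trace in the data described. A confirmed acceptability result is meant to carry the cesarean model into an NIH funding request, so a frequency that misses early removals would feed directly into that decision. Opioid use at home would be missed in the same way, although the protocol itself singles out the period after discharge.

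**Working it through.** The protocol has no sample-size or power calculation and plans no statistical analysis, so there is no figure of its own to reproduce. The check is a reading of the text plus simple counts.

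**Inputs from the protocol**
- Assessments at 12, 24, 48, 72, 96 and 120 h: 6 per woman (Data Collection and Outcome Measures).
- Wear period of five days: 5 × 24 = 120 h (Recruitment).
- Device group: n = 5, so 5 × 6 = 30 planned woman-assessments (Pre-and-Post Metric Evaluation).

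**Input not in the protocol**
- Discharge time D. Discharge before 120 h is foreseen for some women; how long before is not stated. The values below are assumptions, and an assessment due at hour D is taken as done before the woman leaves.

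**Step 1: what falls after discharge.** Assessments not reached = number of scheduled times later than D. Wear time not covered = (120 − D) / 120.

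| Assumed D | Assessments not reached | Wear time not covered |
|---|---|---|
| 96 h | 1 of 6 (17%) | 24/120 = 20% |
| 72 h | 2 of 6 (33%) | 48/120 = 40% |
| 48 h | 3 of 6 (50%) | 72/120 = 60% |

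Only the loss of the 120 h assessment follows from the text, and only for women who go home earlier. If all five left at 72 h, 5 × 2 = 10 of 30 planned woman-assessments would fall after discharge.

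**Step 2: effect on the primary frequency.** One woman is 1/5 = 20 percentage points. If m women have no tolerability report for the end of wear, the gap between counting all of them as successes and all as failures is at most m/5:
- m = 1: 20 points
- m = 3: 60 points
- m = 5: 100 points

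The number of women affected is not in the protocol, so the full range is m = 0 to 5. The gap is a maximum because a woman changes the count only if she also meets the pain component.

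**Step 3: direction.** Suppose the endpoint is judged on in-hospital ratings alone, a woman rated the device excellent on the ward, met the 20% pain decrease, and took the device off early at home because she could not tolerate it. She counts as a success, although she would not if tolerability covered the whole wear period. Under those conditions the error favours the device.

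**Step 4: the controls.** No route to post-discharge data is described for the five January 2019 controls either. Collecting home opioid use for device women alone would put unequal observation periods into the comparison.

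**The case against.** The strongest reply is that the protocol does say the data will be collected at 96 and 120 h, so only the mode of contact is unstated. The standard-of-care label also cannot be meant literally for every item, since ward routine has no established rating for the tolerability of a study device. A research team exists, and readmission is on the list of outcomes, so data capture is not plainly meant to end at discharge.

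Part of this stands. A reader might infer that no post-discharge data will exist and that the last part of a five-day endpoint goes unobserved. The text does not support that: collection is promised, and the endpoint has no stated time point. Five days is the wear period. A reader might also infer that bias towards the device is certain. It is not, because no rule says that in-hospital ratings stand in for later ones, and the handling of missing ratings may be set out in an SAP that is not shown. Discharge at 48, 72 or 96 h is likewise assumed.

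What remains is that the only route named does not reach women whom the same section expects to be at home. How data are obtained is a matter for the protocol. Recording readmissions captures neither tolerability nor the hour of removal.

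**Conclusion.** The point holds in a limited form. For any woman discharged before 120 h, the stated route does not reach the remaining assessments: at least the one at 120 h, and earlier ones depending on length of stay. Late tolerability and early removal at home are therefore not secured. If the endpoint is then judged on in-hospital ratings alone, each woman who removes the device early at home could raise the primary frequency by up to 20 percentage points. That size assumes that she met the pain component, that her ward ratings were excellent, and that early removal would have counted against tolerability. The change is worth making before enrolment. It does not undermine the pilot as a whole.

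**What to change.** In Data Collection and Outcome Measures:

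- Limit the standard-of-care label to assessments made during the hospital stay.
- State that a woman discharged before 120 h fills in a one-page diary at each remaining time point, covering pain at rest and on movement, tolerability, and the hour of and reason for any removal. Existing research staff confirm it in one call at 120 h.
- State that the tolerability component covers the full wear period, and that a woman with no post-discharge report counts as not having excellent tolerability.

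Alternatively, restrict the primary endpoint, and the conclusion drawn from it, to the in-hospital period.

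In either case, limit the pain and opioid comparison with the January 2019 controls to the hospital stay over matching hours. Report any home opioid use descriptively, for device women only.

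The cost is a short protocol change, a diary page and at most one call for each of five women. The downsides are that some data will be self-reported at home and that the tolerability frequency may come out less favourable.

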Official Title: An Open-Label Application of the NSS-Bridge Device for Post-Cesarean Pain

ClinicalTrials.gov ID (NCT number): NCT03830307

Document Date: 2/1/2019

Project Title: Feasibility and Tolerability of the Use of NSS-Bridge Device for Post-Cesarean Pain**Management****Introduction**

The current opioid epidemic has led to a renewed interest in exploring non-pharmacological techniques to treat post-operative pain. An increasing number of patients are suffering from the adverse effects of opioid use following surgery, including post-operative nausea and vomiting, respiratory depression, immunosuppression, constipation, and most recently, addiction. In the United States, over \$600 billion is spent every year on opioid addiction, including \$79 billion related to opioid addiction following surgery. Despite many initiatives to decrease the use of opiates in the preoperative setting, opioids continue to be regularly prescribed before, during and after surgery. Although the risk of opioid addiction following surgery is recognized, the percentage of patients becoming addicted to opioids following surgery is not well understood. To date, there has been virtually no agreement regarding the duration and dosage that qualify for opioid dependence following surgery, nor that a clear estimation of the factors such as biological, psychosocial and socioeconomic that increase the risk of using opioids for extended periods of time after surgery. Therefore, in order to combat this growing health crisis at the ground level, it is incumbent upon the medical community to explore alternative methods of pain control to treat the surgical population in order to reduce the incidence of post-operative opioid addiction.

Project Aims/Goals

Percutaneous Nerve Field Stimulation (PNFS) is one of these recognized methods that ongoing research has shown to be effective as a complementary method of pain management. While PNFS is not a novel concept, clinical indications of auricular field stimulation have been limited in the past due to requirement of bulky, stationary and non-disposable stimulators and electrodes. These technological

limitations made it difficult to establish the real clinical potential of auricular stimulation for the perioperative management of pain in surgical patients, despite the demonstration that auriculotherapy has been shown to relieve pain in the postoperative setting.

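### The historical control group is worded differently in five places, and none fixes where the run of five starts or applies the study's eligibility criteria to it

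*Protocol*

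**What the plan says.** The protocol describes the historical controls in five places.

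- The paragraph just above Specific Aims, and again the end of Data Collection and Outcome Measures: "pain score and opioid consumption will be compared to data obtained 5 consecutive who underwent a C-section the month before". Neither says before what.
- Specific Aims, Aim 2: "five historical consecutive controls of women who underwent cesarean section in January 2019".
- Study Design: "historical controls who have had elective C-Sections in the period of January, 2019".
- The last paragraph of Pre-and-Post Metric Evaluation: "historical controls who have had C-Sections at Magee Womens hospital in January 2019". This paragraph makes the comparison of total perioperative opioid consumption with these controls the measure of efficacy, and adds respiratory depression, PONV, constipation and length of stay.

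On timing, the title page gives "Document Date: 2/1/2019", and Study Design says that "Institutional review board approval will be obtained before eligible patients are recruited and consented". No enrolment date is given. Data Collection and Outcome Measures ties the pilot to a grant application due on 8 March 2019. The study is open-label, has five treated patients, and plans no formal statistical analysis.

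**The concern.** Taking historical controls consecutively guards against selection only if it is settled in advance which case comes first and who qualifies. The protocol settles neither.

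Two things follow. First, the control group need not resemble the treated group. Participants must have an elective cesarean and pass exclusions that include daily preoperative opioid use for severe chronic pain, active anxiety and active drug abuse. These characteristics bear directly on pain scores and opioid consumption, yet most of the control descriptions would admit women who have them, or who had an unplanned cesarean. Second, the run of five could be picked after control and participant outcomes are known, in an open-label study using routinely recorded data. With five women per group and no test, the choice of those five largely determines the comparison that is shown, and the protocol intends the pilot data to support a funding proposal.

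**Working it through.** The protocol gives no sample-size or power figure that depends on this point, so there is nothing to reproduce. The check is a comparison of the texts, followed by an illustration of size.

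**1. The five descriptions side by side**

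| Place | Period | Five? | Consecutive? | Elective? | Start of run | Study criteria applied? |
|---|---|---|---|---|---|---|
| Paragraph above Specific Aims | month before (no reference event) | yes | yes | no | no | no |
| Aim 2 | January 2019 | yes | yes | no | no | no |
| Study Design | January 2019 | no | no | yes | no | no |
| Data Collection and Outcome Measures | month before (no reference event) | yes | yes | no | no | no |
| Pre-and-Post Metric Evaluation | January 2019 | no | no | no | no | no |

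The last two columns are empty throughout, so combining the five descriptions does not fill them.

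**2. Do the two periods conflict?** Read as a US date, the document is dated 1 February 2019, and the month before that is January. The grant deadline is 8 March and follow-up lasts 120 hours, which is 120 / 24 = 5 days. Complete data by the deadline therefore need the last cesarean by about 8 − 5 = 3 March. Enrolment would fall essentially in February, where the two wordings agree. They part only for a woman enrolled in March or later, which the text does not exclude.

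**3. How many runs are open?** If a month holds M eligible cesareans, the number of runs of five consecutive cases is M − 5 + 1 = M − 4. The protocol gives no volume, so M is an assumption.

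**4. How far could deliberate choice move the control mean?** The model is M independent standard-normal outcomes per month with no device effect, taking the largest mean of five consecutive values. The simulations used 20,000 months for M = 40 and 80, and 40,000 for M = 10 and 20.

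| M (assumed) | Runs, M − 4 | Expected mean of the most favourable run, above the true mean |
|---|---|---|
| 10 | 6 | 0.36 SD |
| 20 | 16 | 0.62 SD |
| 40 | 36 | 0.82 SD |
| 80 | 76 | 0.98 SD |

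**5. Yardsticks.** The standard error of a mean of five is 1/√5 = 0.45 SD. The standard error of a five-versus-five difference is √(1/5 + 1/5) = 0.63 SD. At M = 20 the worst-case shift exceeds the first and about equals the second; at 40 and 80 it exceeds both. At M = 10 it is below both.

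**6. The other end.** If the start is fixed, or chosen without regard to outcomes, the expected shift is 0. In the simulation, the first run of the month averaged between −0.006 and 0.002 SD across the volumes tried.

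The effect of admitting non-elective or ineligible controls cannot be put in figures from the document.

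**The case against.** The strongest reply is that the descriptions do not really conflict. Study Design and the closing paragraph can be read as shorter restatements of Aim 2, which supplies the number, the word 'consecutive' and the month. The document date and the grant deadline make January the natural reading of the month before. This largely stands. A reader might infer that the protocol specifies contradictory months or several distinct control groups; the text supports an ambiguity of wording, not a proven contradiction.

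A reader might also infer that the team has read the January charts and means to choose among them. Nothing says so, and no place states who extracts control data or when. The word 'consecutive' already rules out picking individual women. What remains is that the text does not prevent an outcome-informed choice of run.

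The size is a ceiling: it assumes that every run is inspected and the most favourable one taken, at volumes the protocol does not state. Nor does fixing the start remove chance variation; the 0.45 SD standard error stays.

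The consequence is limited too. The main purpose is feasibility and acceptability, Aim 2 looks only for a trend, and no test or decision rule uses the controls.

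Finally, a rule for drawing controls could sit in an SAP that is not shown. That would cover a detail on which the protocol was silent. Here the protocol itself defines the controls, five times and in differing terms, so the wording has to be reconciled there.

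**Conclusion.** The point holds as a low-cost correction to the control definition. The five descriptions differ in period wording, in whether controls are elective, and in whether they are five consecutive women; none anchors the run or applies the study's criteria. The stated efficacy measure therefore rests on a group that could include non-elective or ineligible women and could be selected with outcomes in view.

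The worst-case shift is about 0.6 to 1.0 SD. It rests on 20 to 80 eligible cesareans in the month, independent normal outcomes and deliberate choice of the most favourable run. It should not be read as the expected bias, which is zero for a start chosen blind to outcomes. Nor does the finding undermine the primary end point, which combines tolerability with a pain reduction of at least 20% and is not stated to use the controls.

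**What to change.** Use one definition in all five places, fixed before the first device is applied. For example: the last five consecutive elective cesareans on or before 31 January 2019 that meet the study's inclusion and exclusion criteria, counted backward, with no eligible woman skipped. Another anchor or counting direction would serve equally well if set in advance. Delete the references to the month before.

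Screen eligibility from preoperative records, because a surgical schedule alone would not ordinarily show exclusions such as daily opioid use or anxiety. Lock the list of five before any postoperative pain or opioid data are extracted.

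The cost is one sentence repeated in five places and some chart screening, with no extra participants. The team gives up the freedom to replace a control whose chart is incomplete; her missing values are reported as missing.
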